### 3 ANALYSIS SETS AND SUBGROUPS

#### 3.1 Analysis Sets

Within the framework of this study, the following analysis sets are defined and analysed:

**The Enrolled Set (ES)** will be defined as all patients who provided informed consent.

**The Safety Set (SS)** will be defined as all patients who belong to ES with at least one IMP administration.

**The Full Analysis Set (FAS)** will be defined as all patients who belong to SS with at least one efficacy assessment at visit MPV3.

**The modified Full Analysis Set (mFAS)** will be defined as all patients who belong to FAS with no substantial changes to their regimen of PAH-approved medications (including diuretics) between visits A1 and MPV3. These patients were defined during Data Review (see Data Review Report, Final 1.0, 10-MAR-2022).

**The Pharmacokinetic Analysis Set (PKS)** and **the Pharmacodynamic (PD) Analysis Set**, as well as all corresponding analyses, are described in the reporting and analysis plan prepared by Quotient Sciences Ltd.

Efficacy analyses will be performed on the FAS and mFAS, and the SS will be used for the analysis of the safety endpoints.

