**Table 5: Right Heart Catheterisation Normal Ranges**

Parameter	Normal Range
Cardiac output (L/min) (CO)	2.5-8.0
Mixed venous oxygen saturation (%) (S v O 2 )	60-80
Pulmonary artery pressure systolic (mmHg) (PAPs)	25-80
Pulmonary artery pressure diastolic (mmHg) (PAPd)	8-16
Mean pulmonary artery pressure (mmHg) (mPAP)	≥25
Pulmonary artery wedge pressure (mmHg) (PAWP)	≤15
Right atrial pressure (mmHg) (RAP)	<14
Transpulmonary pressure gradient (mmHg) (TPG)	>12
Diastolic pressure gradient (mmHg) (DPG)	>6
Pulmonary vascular resistance (dyn*s/cm  ) (PVR)	250-1000
Systemic vascular resistance (dyn*s/cm  ) (SVR)	800-1200
Cardiac index (L/min/m  ) (CI)	>2
Pulmonary arterial compliance (mL/mmHg) (PAC; SV/PP)	0.4-3.8
Heart rate (bpm)	50-100
Stroke volume (mL/beat) (SV)	>50
Stroke volume index (mL/m  /beat) (SVI)	>30

Recalculated results will be used for applicable parameters.

The following statistical output will be provided:

Table 15.2.1.1.1 Summary of Right Heart Catheterisation Parameters by HTD – Full Analysis Set

Table 15.2.1.1.2 Summary of Right Heart Catheterization Parameters – Full Analysis Set

Table 15.2.1.1.3 Summary of Right Heart Catheterisation Parameters by HTD – Modified Full Analysis Set

Table 15.2.1.1.4 Summary of Right Heart Catheterization Parameters – Modified Full Analysis Set

The default summary statistics of RHC test results will be presented by HTD and overall at visits A1 and MPV3. The absolute change from baseline will be presented as well. For the changes from baseline a 95% confidence interval will be provided.

Table 15.2.1.1.5 Summary of Right Heart Catheterization Parameters – Modified Full Analysis Set (TAPSE Subgroups)

The default summary statistics of RHC parameters PVR, mPAP, RAP, and CI will be presented by TAPSE subgroup and overall at visits A1 and MPV3. The absolute change from baseline will be presented as well. For the changes from baseline a 95% confidence interval will be provided.

Table 15.2.1.2.1 Incidence of Right Heart Catheterisation Abnormalities – Full Analysis Set

Table 15.2.1.2.2 Incidence of Right Heart Catheterisation Abnormalities – Modified Full Analysis Set

Number and percentage of patients with abnormal values will be displayed by HTD and overall in not CS abnormal and CS abnormal categories. Percentage will be based on the number of patients at specified visit.

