### 5.5.2 6-Min Walk Test (6-MWT)

The 6-MWT is a self-paced test of walking capacity used to assess aerobic capacity and endurance. It plays a key role in evaluation functional exercise capacity, assessing prognosis and evaluating response to treatment across a wide range of respiratory diseases. The distance covered over a time of 6 minutes is used as the outcome by which to compare changes in performance capacity.

The test will be performed at visit V1 before IMP intake and at visit MPV3 before right heart catheterisation.

At screening, two attempts must be performed, separated by at least 30 minutes. The attempt in which the longer distance was covered will be considered as baseline. In case the distance covered during both attempts is equal, the first attempt will be considered as baseline.

The following parameters will be collected:

- SpO2 (%) – before and after the test
- Borg Dyspnoea score – before and after the test
- Heart rate (bpm) – before and after the test
- Lap length (m)
- Number of laps completed
- Distance covered (m)
- Time walking (min)
- Oxygen flow rate (L/min)
- Number of stops
- Time stopped (min)

The Borg Dyspnoea score is a patient-reported measure for assessing breathlessness. Symptoms of breathlessness are rated on a scale of 0-10, where 0 indicates no symptoms and 10 indicates the most severe breathlessness.

The differences in SpO2, the Borg Dyspnoea score, and heart rate between after and before the test will be calculated. These differences will be displayed as additional parameters in summaries.

The following statistical output will be provided:

Table 15.2.2.1 Summary of 6-MWT by HTD – Full Analysis Set

Table 15.2.2.2 Summary of 6-MWT – Full Analysis Set

Table 15.2.2.3 Summary of 6-MWT by HTD – Modified Full Analysis Set

Table 15.2.2.4 Summary of 6-MWT – Modified Full Analysis Set

The default summary statistics of 6-MWT test results will be presented by HTD and overall at visits V1 and MPV3. The absolute change from baseline will be presented as well. For the changes from baseline a 95% confidence interval will be provided.

Table 15.2.2.5 Summary of 6-MWT Distance – Modified Full Analysis Set (TAPSE Subgroups)

The default summary statistics of 6-MWT distance travelled will be summarised by TAPSE subgroup and overall at visits V1 and MPV3. The absolute change from baseline will be presented as well. For the changes from baseline a 95% confidence interval will be provided.

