### 5.5.4 Echocardiography

Transthoracic echocardiography is used to image the effects of PAH on the heart. An echocardiogram (ECHO) will be performed at Visit 1 and MPV3.

The following parameters will be determined:

- Tricuspid regurgitation (absent, mild, moderate or severe)
- Right ventricular contractility (TAPSE) (mm)
- Pericardial effusion (absent, traces or present)
- Right atrial area (end-systolic) (cm^2)
- Right ventricular end-diastolic area (cm^2)

The clinical significance (yes/no) of any abnormal ECHO findings will be assessed by the investigator.

The following statistical output will be provided:

Table 15.2.4.1.1 Summary of Categorical Echocardiography Parameters – Full Analysis Set

Table 15.2.4.1.2 Summary of Categorical Echocardiography Parameters – Modified Full Analysis Set

Number and percentage of patients will be displayed by HTD and overall at visits V1 and MPV3. Percentage will be based on the number of patients at the specified visit.

Table 15.2.4.2.1 Summary of Numerical Echocardiography Parameters by HTD – Full Analysis Set

Table 15.2.4.2.2 Summary of Numerical Echocardiography Parameters – Full Analysis Set

Table 15.2.4.2.3 Summary of Numerical Echocardiography Parameters by HTD – Modified Full Analysis Set

Table 15.2.4.2.4 Summary of Numerical Echocardiography Parameters – Modified Full Analysis Set

The default summary statistics of ECHO parameters will be presented by HTD and overall at visits V1 and MPV3. The absolute change from baseline will be presented as well. For the changes from baseline a 95% confidence interval will be provided.

Table 15.2.4.2.5 Summary of Numerical Echocardiography Parameters – Modified Full Analysis Set (TAPSE Subgroups)

The default summary statistics of ECHO parameters will be presented by TAPSE subgroup and overall at visits V1 and MPV3. The absolute change from baseline will be presented as well. For the changes from baseline a 95% confidence interval will be provided.

Table 15.2.4.3.1 Incidence of Echocardiography Abnormalities – Full Analysis Set

Table 15.2.4.3.2 Incidence of Echocardiography Abnormalities – Modified Full Analysis Set

Number and percentage of patients will be displayed by HTD and overall in Not CS abnormal and CS abnormal categories. Percentage will be based on the number of patients at the specified visit.

Table 15.2.4.4.1 Shift Table of Echocardiography Results – Full Analysis Set

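### The three TAPSE subgroup tables are planned only on the mFAS, a set selected on post-baseline therapy changes, with no FAS version beside them

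*SAP*

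**What the plan says.** SAP 3.1 builds the mFAS from FAS patients with "no substantial changes to their regimen of PAH-approved medications (including diuretics) between visits A1 and MPV3" and adds: "These patients were defined during Data Review". For the criterion it points to the Data Review Report; the SAP does not say what counts as a substantial change. The same section gives the general rule: "Efficacy analyses will be performed on the FAS and mFAS, and the SS will be used for the analysis of the safety endpoints".

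SAP 3.2 forms two subgroups from TAPSE at V1, split at 17 mm, to explore how right ventricular dysfunction at baseline bears on selected efficacy parameters. It says subgroup analyses are done where Section 5 calls for them, because not every endpoint may need one. It does not mention an analysis set.

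Section 5 calls for them three times:

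- SAP 5.5.1, for PVR, mPAP, RAP and CI: "Table 15.2.1.1.5 Summary of Right Heart Catheterization Parameters – Modified Full Analysis Set (TAPSE Subgroups"
- SAP 5.5.2: "Table 15.2.2.5 Summary of 6-MWT Distance – Modified Full Analysis Set (TAPSE Subgroups"
- SAP 5.5.4, as Table 15.2.4.2.5: "Summary of Numerical Echocardiography Parameters – Modified Full Analysis Set (TAPSE Subgroups"

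Each gives summary statistics at both visits and the change from baseline with a 95% confidence interval, by subgroup and overall. Protocol section 13.4.2 bases efficacy on the FAS and has neither an mFAS nor TAPSE subgroups.

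**The concern.** TAPSE at V1 is a baseline feature. Staying in the mFAS depends on what happened to background therapy between A1 and MPV3. If substantial therapy changes are more frequent in one TAPSE subgroup, or of a different kind, the mFAS removes different sorts of patients from the two columns. The tables could then show a pattern by right ventricular function that partly reflects who was removed, or could hide a real one.

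For the unsplit summaries a reader can set the FAS beside the mFAS and see whether the exclusion matters. For the TAPSE tables that check is missing, and the overall FAS tables cannot supply it because they are not split by TAPSE. What is at stake is how an exploratory pattern is read. No test or error rate is involved.

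**Working it through.** **1. Which tables exist on which set** (SAP 5.5.1, 5.5.2 and 5.5.4, checked against the output list in SAP 10.1, where the TAPSE tables are items 49, 58 and 71):

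| Parameters | FAS, unsplit | mFAS, unsplit | TAPSE on mFAS | TAPSE on FAS |
|---|---|---|---|---|
| Catheterisation | 15.2.1.1.1, 15.2.1.1.2 | 15.2.1.1.3, 15.2.1.1.4 | 15.2.1.1.5 | none |
| 6-MWT | 15.2.2.1, 15.2.2.2 | 15.2.2.3, 15.2.2.4 | 15.2.2.5 | none |
| Numerical echocardiography | 15.2.4.2.1, 15.2.4.2.2 | 15.2.4.2.3, 15.2.4.2.4 | 15.2.4.2.5 | none |

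So 3 of 3 TAPSE tables are on the mFAS and 0 of 3 on the FAS. No reason appears in SAP 3.1, 3.2 or the 5.5 subsections. SAP 8 records no changes from the protocol's analysis, so it gives none either.

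**2. What the selection can do.** The plan gives no figure to reproduce: the 32 patients were not formally calculated, and no SD or rate of therapy change is stated. The following is an illustration under assumptions.

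Let f be the share of FAS patients excluded from the mFAS, and d the mean change in retained minus excluded patients, in SD units. The FAS mean is (1 − f) × retained mean + f × excluded mean, so

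mFAS mean − FAS mean = f × d.

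- f = 0.10, d = 0.5: 0.05 SD
- f = 0.30, d = 1.0: 0.30 SD

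With the same d in both subgroups, the contrast between them shifts by (f in TAPSE ≤ 17 − f in TAPSE > 17) × d:

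- 20% versus 10%, d = 0.5: 0.10 × 0.5 = 0.05 SD
- 40% versus 10%, d = 1.0: 0.30 × 1.0 = 0.30 SD

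**3. Scale.** The 95% half-width for one subgroup mean is t(0.975, n − 1)/√n:

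- n = 16 (all 32 patients, even split assumed): 0.53 SD
- n = 11 (about 30% fewer): 0.67 SD

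The assumed shift lies below one subgroup's sampling error at every setting. At the top of the range it is more than half of it (0.30/0.53 = 0.57), and the interval does not reflect it.

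**4. Can the direction be fixed?** Take PVR in dyn·s/cm⁵. Assume a mean change of −30 in patients with stable therapy in both subgroups and w in those whose therapy changed. The mFAS contrast is then 0 by construction. The all-patient contrast (≤ 17 minus > 17) is (p₁ − p₀) × (w + 30), with p₁ = 0.2 to 0.4 and p₀ = 0.1:

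- w = +60, p₁ = 0.2: 0.1 × 90 = +9
- w = +120, p₁ = 0.4: 0.3 × 150 = +45
- w = −100, p₁ = 0.2: 0.1 × (−70) = −7
- w = −100, p₁ = 0.4: 0.3 × (−70) = −21

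The sign depends wholly on w. If therapy changes accompany worsening that persists to MPV3, w is high. If the added therapy has lowered PVR by MPV3, w is low. The documents do not say which.

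**The case against.** **The mFAS has a legitimate purpose.** There is no control arm. On the FAS, a change from baseline mixes any effect of zamicastat with that of altered background drugs or diuretics. Restricting to stable background therapy is a reasonable exploratory choice. This stands, and it is why the FAS should not simply be declared the main version.

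**The FAS is also selected after baseline.** The SAP's FAS requires at least one efficacy assessment at MPV3, whereas protocol section 13.2.2 asks only for one IMP administration. Catheterisation, walk test and echocardiography are not done at early discontinuation (protocol section 11.6.7). Patients who withdrew are missing from these summaries on either set. This stands too and limits what the fix achieves.

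**No formal contrast is planned.** The tables describe change within each subgroup, with no test or interaction, in about 32 patients. That lowers the stakes. The declared purpose is still to explore the role of right ventricular dysfunction, and readers will compare the two columns.

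**The information is available elsewhere.** Table 15.1.1.2 gives reasons for exclusion, Listing 16.2.1.4 the excluded patients, and other listings the individual efficacy values and medications. With so few patients, FAS subgroup values could be rebuilt by hand. However, no planned summary splits the exclusions by TAPSE, and the PAH-approved therapy tables are by HTD and overall.

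**SAP 3.2 allows selectivity.** It does so for endpoints. It does not restrict the analysis set, so it does not explain the departure from 3.1.

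**Conclusion.** The gap is real and modest. All three TAPSE tables rest on a set chosen by a post-baseline event, contrary to SAP 3.1 and protocol section 13.4.2, without explanation. This could distort the apparent pattern by right ventricular function if therapy changes differ between the subgroups. The 0.05–0.30 SD shift rests entirely on assumed exclusion rates and outcome differences, so neither size nor direction can be determined from the documents.

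Three stronger readings are tempting and not supported:

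- *That the mFAS flatters the TAPSE ≤ 17 mm subgroup by removing patients who worsened.* The documents do not say that therapy changes mark worsening or cluster in that subgroup. A reduction, or a switch for intolerance, could also count as a substantial change, and the sign reverses under plausible values.
- *That the set was chosen to suit the results.* The revision history shows the mFAS and the TAPSE subgroups entering together in Draft 0.4, after the Data Review meeting of this open-label study. That is a reason for showing both sets. It is not evidence of intent, and the SAP states that it is finalised before analysis begins.
- *That the FAS tables would be the unbiased answer.* They would still require an MPV3 assessment and would include the effects of altered background therapy.

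**What to change.** Produce Tables 15.2.1.1.5, 15.2.2.5 and 15.2.4.2.5 on the FAS as well, beside the mFAS versions and in the same layout. Add a short count by TAPSE subgroup: number in the FAS, number excluded from the mFAS, and type of therapy change (escalation, reduction or switch). SAP 5.3 already collects drug, daily dose and start and stop dates, so no new data are needed. Restate in the SAP the criterion for a substantial change that was applied at Data Review.

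Label both versions exploratory and read them together. If they agree, the exclusion made little difference to the pattern. If they differ, the counts show where to look. Add a footnote that the FAS requires an efficacy assessment at MPV3, so one layer of selection remains.

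The cost is three repeat descriptive tables, one small count table and the matching entries in SAP 10.1. The downside is more output with small subgroups and wide intervals. Sample size and error rates are unaffected. If the SAP is not reopened, the additions can be described and justified in the final report, as protocol section 13.5 provides for deviations from the SAP.

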#### 3.2 Subgroup Analysis

Subgroups will be formed to explore the effects of right ventricular dysfunction at baseline on selected efficacy parameters based on echocardiography results at V1. The subgroups are described in Table 2 below.

Statistical analyses using subgroups will be conducted when specifically referred to in relevant subsections of Section 5, as not every endpoint might need further evaluation using subgroups.

**Table 2: Subgroup Labels**

Number	Description	Label in TLFs
1	Right ventricular contractility (TAPSE) $\leq$ 17 mm	TAPSE $\leq$ 17 mm
2	Right ventricular contractility (TAPSE) $>$ 17 mm	TAPSE $>$ 17 mm

## 4 GENERAL DEFINITIONS AND NAMING CONVENTIONS

In order to avoid ambiguity during the analysis, a number of definitions and conventions for data handling are described here.

### 4.1 General Methodology and Presentation of the Results

The default summary statistics for quantitative (continuous) variables will be

- the number of patients (n),
- mean,
- standard deviation (SD),
- coefficient of variation (%CV),
- median,
- minimum (min) and maximum (max)

for patients with data.

Mean and median will be presented to one more decimal place than the raw value. The minimum and maximum values will be presented with the same decimal precision as the raw value. SD will be reported to two decimal places greater than the original value, however no more than 3 decimal places will be presented. CV will be reported to one decimal place.

For qualitative (categorical) variables, the frequency count (n) and percentage (%) of patients with non-missing data per category will be the default frequency tabulations. Where appropriate and present, the number of missing values will be displayed as “Missing” category.

Percentage values are to be presented to one decimal place, for example, 52.3%.

The denominator used for calculation of the percentages will be specified in a footnote to the tables for clarification.

### 4.2 Statistical Output Layout

All titles and column headers (consisting of one or several words) will be capitalised; articles, prepositions, and conjunctions, and “To” in infinitives will not be capitalised, except they are at the beginning of titles or headers.

All pages will be numbered according to the table/listing/figure to which the page belongs to. Every table/listing/figure will be numbered from page 1, “Page X of Y” at the bottom of each page.

The definition of baseline value will be described in a footnote in every TLF where applicable. Other important definitions will also be presented if necessary.

Dates will be listed in the format: yyyy-mm-dd (e.g. 2003-11-20). Times will be listed in the format: hh:mm (e.g. 09:15) or in the format hh:mm:ss if seconds are collected. When date and time are collected, these are listed in the format: yyyy-mm-ddThh:mm (e.g. 2003-11-20T09:15), yyyy-mm-ddThh, or yyyy-mm-ddThh:mm:ss.

Partial missing dates will be listed in the format yyyy-mm (e.g. 2013-11) if only day is missing or in the format yyyy (e.g. 2013) if month and day are missing.

Missing data including missing dates or times will be displayed in listings as blank fields, unless otherwise specified.

Listings will be sorted by patient’s number and visit number where applicable, unless specified otherwise.

### 4.3 Dose Group Names and Labels

Statistical output for baseline characteristics, as well as visit-based safety and efficacy evaluations, will be presented by dose groups. Patients will be allocated to a particular dose group based on their individual HTD, while patients that do not tolerate the 50 mg dose will be allocated to the “No HTD” group for analysis by HTD.

Adverse events and concomitant medications will be summarised based on the concurrent IMP dose, without allocating patients to separate dose groups. Details of assignment of concurrent IMP doses will be further described in the Sections 5.3 and 5.6.1.

The labels to be used in the tables, listings and figures are defined in the table below.

**Table 3: Dose Group Labels**

Description	Label in TLFs	
	By Concurrent Dose	By HTD
Dose A: 50 mg zamicastat once daily (half a tablet of 100 mg)	ZMC 50 mg	No HTD HTD 50 mg
Dose B: 100 mg zamicastat once daily (one tablet of 100 mg)	ZMC 100 mg	HTD 100 mg
Dose C: 150 mg zamicastat once daily (one and a half tablet of 100 mg)	ZMC 150 mg	HTD 150 mg
Dose D: 200 mg zamicastat once daily (two tablets of 100 mg)	ZMC 200 mg	HTD 200 mg

#### 4.4 Visit Names and Labels

This SAP covers only visits which are part of the core study. The extension study (BIA-51058-202) will be covered in a dedicated SAP. The names to be used in the analysis datasets and the labels to be used in the tables, listings and figures for the different study visits are defined below.

**Table 4: Visit Names and Labels**

Period	Number	Name	Description	Label in TLFs
Screening	100	Visit 1	Screening visit. Day -12 to -5	V1
Dose finding	110	Visit A1	Day 1	A1
	120	Visit A2	8 days $\pm$ 2 after A1 (phone call)	A2
	130	Visit A3	14 days $\pm$ 2 after A1	A3
	220	Visit B2	8 days $\pm$ 2 after A3 (phone call)	B2
	230	Visit B3	14 days $\pm$ 2 after A3	B3
	320	Visit C2	8 days $\pm$ 2 after B3 (phone call)	C2
	330	Visit C3	14 days $\pm$ 2 after B3	C3
	420	Visit D2	8 days $\pm$ 2 after C3 (phone call)	D2
Maintenance	430	Visit D3	14 days $\pm$ 2 after C3	D3
	510	Visit MPV1	13 days $\pm$ 2 after D3/UV for down-titration	MPV1
	520	Visit MPV2	27 days $\pm$ 2 after D3/UV for down-titration	MPV2
Dose finding/ Maintenance	530	Visit MPV3	41 days $\pm$ 2 after D3/UV for down-titration	MPV3
	600	Early Discontinuation Visit	Within 10 days of early discontinuation	EDV
Follow-up	610	Follow-up visit [down-titration]	14 days $\pm$ 2 after MPV3/EDV (phone call)	FUV1
	620	Follow-up visit	14 days $\pm$ 2 after last IMP intake	FUV2

Unscheduled visits (UV) will be numbered and labelled based on the preceding scheduled visit, e.g. "UV A1.1" for the first unscheduled visit after the scheduled visit A1. Multiple unscheduled visits after the same scheduled visit will be numbered and labelled sequentially.

For patients attending the extension study, adverse events and concomitant medications will only be displayed up to the end date of visit MPV3.

## 4.5 Day Numbering

All assessment dates will be related to the date of first IMP intake. The date of first IMP intake is referred to as Day 1. Day -1 is the day preceding Day 1 and Day 0 will not be defined. The numbering is such that Day -2 is the day before Day -1, Day 2 is the day after the first IMP intake, etc.

Treatment days may alternatively be numbered with reference to the ongoing study period using the following rules:

- Dates prior to the first IMP intake will be numbered with reference to the date of first IMP intake as described above.
- Dates after the first IMP intake will be numbered with reference to the first day of the ongoing study period using the same rules as described above. Study days during the dose-finding period will be prefixed with the corresponding dose letter (e.g. C-11 for day 11 on the 150 mg dose), study days in the maintenance period will be prefixed with the letter M, and study days in the post-maintenance periods will be prefixed with “DT” and “FU” for the down-titration period and the follow-up period respectively.

For definitions of the study periods, see section 4.6.

